#### 4. Statistical Analysis and Reporting

This SAP is based on the approved clinical study protocol, version 6.0, dated 12-Jun-2023.

This SAP addresses the safety and efficacy objectives of the study and describes the statistical methods that are to be used for the interim and final analysis of the completed study.

The reader of this SAP is encouraged to also read the clinical protocol, Drug Safety and Monitoring Board (DSMB) charter, and any other identified documents, for details on the planned conduct of the study. Operational aspects related to collection and timing of planned clinical assessments are not repeated in this SAP unless relevant to the planned analysis.

#### 4.1. Introduction

Data processing, tabulation of descriptive statistics, calculation of inferential statistics, and graphical representations will be performed primarily using SAS (release 9.4 or higher). If the use of other software is warranted, the final statistical methodology report will detail what software was used for what purposes.

Continuous (quantitative) variable summaries will include the number of participants (n) with non-missing values, mean, standard deviation (SD), median, minimum, and maximum. Other statistics such as coefficient of variation (%CV), quartiles, confidence intervals (CIs), and number of missing values may be added as appropriate.

Categorical (qualitative) variable summaries will include the frequency and percentage of participants who are in the particular category or each possible value. In general, the denominator for the percentage calculation will be based upon the total number of participants in the study population within each treatment group, unless otherwise specified. The denominator for by-visit displays will be the number of participants in the relevant study population with non-missing data at each visit.

The minimum and maximum will be reported with the same degree of precision (i.e., the same number of decimal places) as the observed data. Measures of location (mean and median) will be reported to 1 degree of precision more than the observed data. Measures of spread (SD) will be reported to 2 degrees of precision more than the observed data.

Percentages will be presented to 1 decimal place, unless otherwise specified.

Unless otherwise indicated, all statistical tests will be conducted at the 0.05 significance level using 2-tailed tests, and P-values will be reported. A P-value of  $\leq$ 0.10 but >0.05 will be considered evidence of a trend. Corresponding 95% CIs will be presented for statistical tests.

### 4.2. Interim Analysis and Data Monitoring

After the first 24 participants have been randomized and completed their last study visits, the database for those participants will be frozen for purposes of an unblinded interim analysis of safety and efficacy data. All statistical outputs planned for the final analysis at the time of the interim analysis will be generated for the interim analysis. After the data for the first 24 participants is frozen, the unblinded statistician will provide randomization codes for these

participants only. These outputs will exclude any data from participants that are not part of the first 24 randomized participants. The data from the first 24 participants will also be included in the analysis of the final dataset.

A DSMB will oversee the safety of the trial. This committee will consist of independent experts, including an independent statistician. Safety data will be provided to the DSMB at quarterly intervals during the trial. The study clinician and study medical monitor will review trial safety data biweekly and more frequently as the safety data warrant. Similarly, more frequent ad hoc meetings of the DSMB will occur if ongoing safety data indicate interim meetings are indicated. Additional details can be found in the DSMB charter.

#### 5. Analysis Populations

The following analysis populations are planned for this study:

- All Subjects: The All Subjects population includes all participants who sign the ICF and get screened for the study.
- Safety Population (SAF): The Safety Population includes all participants who receive one or more doses of study medication.
- Efficacy Modified Intent-To-Treat Population (mITT): The Efficacy mITT Population includes all randomized participants who receive any amount of study drug and who have a baseline and at least one post-baseline assessment of the ADAS-Cog 11 total score.
- Completers Population (CP): The Completers Population includes all randomized participants who completed the study (i.e., who did not prematurely withdraw). There is no expectation that a participant included in the CP will have attended every single scheduled visit; as long as the participant completed the study, they will be included in the population.
- **Pharmacokinetic Population (PK):** The Pharmacokinetic Population includes all participants in the SAF who had at least one quantifiable concentration of CT1812.

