#### 3.2. Sample Size and Power

The sample size justification in the protocol was as follows: for this trial, groups of 48 active-dosed participants per dose level are felt to give adequate sensitivity to detect AEs. A sample size of 48 active-dosed participants for each dose level (100 mg/day, 300 mg/day) has 91% power to detect at least one occurrence of any drug-related AE with a true prevalence in the treated population of 5%.

Additional participants may be added to replace participants with significant disruption to their visit schedule due to COVID or if there are unanticipated dropouts.

Additionally, for the primary exploratory efficacy analysis relating to the ADAS-COG 11 comparing the combined CT1812 treatment groups versus the placebo group, 48 participants per group provides 81% power to show a treatment difference of 3.0 points assuming a two-sided test at the alpha=0.05 level of significance, assuming a SD of 5.4 points, and a dropout rate of 15%.

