#### 3.5. Method of Assigning Participants to Treatment Groups

Participants will be randomized in a 1:1:1 ratio to CT1812 100 mg/day, CT1812 300 mg/day or placebo. The placebo will be identical in appearance to the active CT1812. The unblinded statistician assigned to the trial will generate a randomization list with the appropriate number of 4--digit individual study identification numbers (IDs) for each arm, randomly assigned to one of the treatment arms.

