#### 6.1.3. Multiple Comparisons

Although all of the clinical efficacy analyses for this study are exploratory in nature, the ADAS-Cog 11 least square mean change from baseline analysis is considered the primary exploratory analysis of interest compared to the other clinical efficacy analyses. The primary exploratory analysis of the ADAS-Cog 11 will compare the least square mean change from baseline value for the two active arms combined to the least square mean change from baseline value for the placebo arm at day 182, using a two-sided test at the alpha=0.05 level of significance. If the primary exploratory analysis of the ADAS-Cog 11 is statistically significant, then the following comparisons will be made using the least square mean change from baseline values and the same model as for the primary analysis:

- 1) 300 mg CT1812 versus placebo;
- 2) 100 mg CT1812 versus placebo.

Each comparison will be conducted using a two-sided test at the alpha=0.05 level of significance. This fixed sequence testing procedure will control the overall level of significance for this outcome.

All other clinical efficacy analyses will be conducted using two-sided tests at the alpha=0.05 level of significance. No adjustments will be made for multiple comparisons and all other p-values will be considered nominal.

[figure not shown]

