    - If  $6 \le$  number cancellation item score  $\le 11$  then re-scale as 4
    - If  $0 \le \text{number cancellation item score} \le 5 \text{ then re-scale as } 5$ 
      - Number cancellation item scores < 0 will be re-scaled as 5
  - The resulting final number cancellation item score will range from 0 to 5.
- The ADAS-13 total score will be derived as the sum of the 13 individual items, but using the score for the number cancellation item which has been re-derived as described above.
- The ADAS-11 total score is the sum of 11 individual items excluding delayed recall and number cancellation.
- The Cognitive Composite score will be calculated using z-scores of the below items. The z-scores will be derived by calculating the baseline mean and standard deviation of each individual component for all participants. A z-score within each component will be derived for each participant at each timepoint by subtracting the corresponding baseline mean and then dividing by the corresponding baseline SD. The Cognitive Composite score will be set as the mean of the 10 individual z-scores (5 ADAS-COG scores and 5 NTB scores) within each participant and timepoint. If a participant is missing one, two, or three scores at a particular timepoint, the missing scores will be set as the average non-missing z-score of all participants at that timepoint within each component when deriving the Cognitive Composite score. If a participant is missing four or more individual components at each timepoint, the Cognitive Composite score will not be derived.
  - o ADAS-COG
    - Word recall (scored on a 0 to 10 range), average of trials I, II, and III. If at least one of the trials is missing, this component will be considered missing. The sign of the z-score for this component will be reversed when deriving the Cognitive Composite score as it is the total words not recalled that is being recorded. This test is a key measure of episodic memory.

- Orientation (0 to 8). The sign of the z-score for this component will be reversed when deriving the Cognitive Composite score as the recorded score for this test is the number of items answered incorrectly. This measure is an index of the study participant's episodic memory and a single item of semantic memory (their name).
- Delayed Word Recall (0 to 10). The sign of the z-score for this component will be reversed when deriving the Cognitive Composite score as it is the total words not recalled that is being recorded.

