#### 8. Efficacy Analysis

All efficacy analyses are exploratory in nature. The intent of this plan is to run the analysis of covariance (ANCOVA) model described in section 8.1 at the time of the interim analysis and the mixed-model repeated measures (MMRM) model described in section 8.1 at the time of the final analysis. However, if the MMRM model fails to converge, the ANCOVA analysis (with both observed and observed + LOCF values) will be run in place of the MMRM model for the final analysis. A Day 182 visit will be considered out-of-window if it does not occur between study day 171 and study day 193 (inclusive).

For the final analysis, all efficacy analyses will be run using the mITT population and a subset of the efficacy parameters (ADAS-Cog 11, ADCS-ADL, MMSE, ADCS-CGIC) will be summarized using the Completers Population as a sensitivity analysis.

All figures will be based on the mITT population only. The following figures will be produced for each efficacy parameter (ADAS-Cog 11, ADCS-ADL, MMSE, ADCS-CGIC and the composite z-scores: Cognitive Composite score; Memory Composite score; Attention Composite score; and Executive Function Composite score):

- Line plot of change from baseline values.
- Line plot of least square mean change from baseline values.
- By-participant spaghetti plots of the change from baseline values.

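### The main analyses of ADCS-ADL, ADCS-CGIC, MMSE, the NTB and the composite z-scores admit only participants with a baseline and a post-baseline ADAS-Cog 11 total

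*SAP*

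**What the plan says.** SAP 5 defines the efficacy mITT population as randomised participants who took any study drug and have a baseline and "at least one post-baseline assessment of the ADAS-Cog 11 total score". SAP 8 then states that, for the final analysis, "all efficacy analyses will be run using the mITT population", and bases all figures on the mITT population alone. SAP 10 describes the mITT analysis as the primary analysis of efficacy data.

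SAP 8.2, 8.3, 8.5 and 8.6 analyse MMSE, ADAS-Cog, ADCS-CGIC and ADCS-ADL in both the mITT and the Completers Populations, with subgroup analyses in the mITT population. SAP 8.1 (composite z-scores) and 8.4 (NTB) mention no second population, so only the general mITT rule applies to them. SAP 8.8 (biomarkers) names no population. The Completers Population in SAP 5 requires study completion and has no ADAS-Cog condition. The protocol (15.3) defines only the safety population.

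On scoring, SAP 6.1.8 says: "The ADAS-11 total score is the sum of 11 individual items excluding delayed recall and number cancellation". It gives no rule for a total with an unscored item. For the ten-component Cognitive Composite, by contrast, SAP 6.1.4 and 6.1.8 allow up to three missing components.

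**The concern.** ADCS-ADL is reported by an informant and ADCS-CGIC is rated by a clinician. Neither depends on the participant having completed the ADAS-Cog. Even so, a participant with ADCS-ADL or ADCS-CGIC ratings at Day 42, 98 or 182 and no ADAS-Cog 11 total is removed from the main analyses of both. For ADCS-CGIC the restriction is harder to justify still. Its model has no baseline covariate (SAP 8.5), yet a missing baseline ADAS-Cog 11 total also excludes the participant.

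Two things are at stake. Observed values that the repeated-measures model could use are discarded. And membership of the analysis set depends on something that happens after randomisation, which can unbalance the arms on endpoints for which the condition serves no purpose.

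**Working it through.** **1. Who is lost.** The cognitive tests, ADCS-ADL and ADCS-CGIC share the same post-baseline visits: Days 42, 98 and 182 (SAP Table 1). Early-termination visits before Day 170 are listed only (SAP 6.1.6). Taking each case:

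- Someone who leaves before Day 42 supplies no modelled efficacy value under either definition, so nothing is lost.
- Someone with one post-baseline ADAS-Cog 11 total, and a baseline one, stays in for all endpoints.
- Someone with an ADAS-13 total also has the 11 items, so ADAS-13 loses nobody.
- Someone with ADCS-ADL, ADCS-CGIC, MMSE or NTB data at a scheduled visit, but no ADAS-Cog 11 total at baseline or at any later visit, is dropped from the mITT analyses of those endpoints. If that person completes the study, the Completers analyses of ADCS-ADL, ADCS-CGIC and MMSE recover the data. If that person withdraws after Day 42 or 98, neither population includes them. The NTB and composite data are not recovered in either case.

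**2. The plan's own power figure.** SAP 3.2 says "48 participants per group provides 81% power to show a treatment difference of 3.0 points", "comparing the combined CT1812 treatment groups versus the placebo group", with SD 5.4, 15% dropout and a two-sided 0.05 test. Allocation is 1:1:1 (SAP 3.5).

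- Evaluable: 48 × 0.85 = 40.8 placebo and 2 × 40.8 = 81.6 pooled active, 122.4 in all.
- SE = 5.4 × √(1/40.8 + 1/81.6) = 1.035.
- Power = Φ(3.0/1.035 − 1.96) = 82.6%. The noncentral t gives 82.0%; with 40 against 80 it gives 81.2%.

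The stated 81% is reproduced. The point here does not alter it, because a participant with no post-baseline ADAS-Cog 11 total adds nothing to the ADAS-Cog 11 model.

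**3. Precision lost on the other endpoints.** The documents give no exclusion rate, and no SD or effect size for these endpoints. Assume that a share x of otherwise evaluable participants is removed by this condition alone. The standard error is then multiplied by 1/√(1 − x). The power column uses the ADAS-Cog 11 inputs purely as a stand-in.

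| x (assumed) | participants (x × 122.4) | SE increase | stand-in power |
|---|---|---|---|
| 0 | 0 | 0 | 82.6% |
| 1% | 1.2 | 0.5% | 82.2% |
| 2% | 2.4 | 1.0% | 81.8% |
| 5% | 6.1 | 2.6% | 80.6% |
| 10% | 12.2 | 5.4% | 78.5% |

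**4. Bias.** Let f be the excluded share of an arm and D the excluded-minus-included difference in mean outcome. Dropping the excluded moves that arm's mean by −fD, so the active-minus-placebo contrast moves by −(f_active × D_active − f_placebo × D_placebo). If f and D are the same in both arms, this is zero. With a common D of 0.5 to 1.5 SD (assumed):

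- 5% against 2%: 0.03 × D = 0.015 to 0.045 SD.
- 10% against 2%: 0.08 × D = 0.04 to 0.12 SD.

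On the raw scale, suppose 2 of 48 placebo participants are excluded, with ADCS-ADL change 10 points worse than the rest of their arm. The placebo mean moves by 2/48 × 10 = 0.42 points on a 0 to 78 scale. These are simple-mean calculations; the effect in the repeated-measures model would be similar in kind but not identical.

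**The case against.** The best defence is that one common population, anchored on the lead exploratory endpoint, keeps denominators the same across tables, and that little depends on it. All efficacy analyses are exploratory (SAP 8), p-values outside the ADAS-Cog 11 sequence are nominal (SAP 6.1.3), population counts are reported by arm (SAP 7.1) and all data are listed (SAP 6.1.9). That is fair. It limits the consequence but gives no reason for the condition on the other scales.

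A reader might also infer more than the documents support:

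- **That every efficacy analysis is affected.** The Completers analyses of ADCS-ADL, ADCS-CGIC, MMSE and ADAS-Cog have no ADAS-Cog condition. They are only a partial remedy, because completion is itself a post-randomisation event and the NTB and composites are not covered.
- **That the biomarker analyses use the mITT population.** Section 8.8 sits under the efficacy heading, but biomarkers are pharmacodynamic endpoints (SAP 2.2.3), are absent from the efficacy endpoint list (SAP 2.2.2), and are given no population. What the text supports is that their population is unspecified.
- **That exclusion tracks impairment.** This is plausible for a performance test, but nothing in the documents says so. Poor performance is scored rather than left missing: word recall counts words not recalled, and orientation counts wrong answers (SAP 6.1.8). Entry requires MMSE 18 to 26 and the ability to complete all screening evaluations (protocol 9.2).
- **That a single unscored item excludes a participant.** The SAP has no missing-item rule, so this is possible. For someone with a baseline total, though, the total would still have to be missing at all three post-baseline visits.

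**Conclusion.** The point holds as a minor one. By the SAP's stated rules, the main, subgroup and figure outputs for ADCS-ADL, ADCS-CGIC and MMSE, and the only analyses of the NTB components and composite z-scores, depend on a baseline and a post-baseline total of a different scale. The condition gives those endpoints no benefit and can discard observed data.

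The affected group is probably small, because the scales share visits and early leavers contribute nothing under either definition. With an assumed 1 to 5% excluded (about 1 to 6 of 122 evaluable participants), standard errors rise by 0.5 to 2.6%. Bias would need differences between arms, and in the assumed cases shown it stays between 0.015 and 0.12 SD. The exclusion rates and the size of D are assumptions, not figures from the documents. No stated figure is shown to be wrong. Separately, the population for the biomarker analyses, which serve the secondary objective, is not named.

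**What to change.** In SAP 5 and 8, analyse each endpoint in all randomised, dosed participants who have a baseline value of that endpoint (where one exists) and at least one post-baseline value of it. Keep the ADAS-Cog 11 condition for the ADAS-Cog 11 analysis only. In SAP 8.8, state that the same endpoint-specific rule applies to each plasma and CSF biomarker. Requiring a post-baseline value of the endpoint itself costs nothing, because a participant without one adds no observation to that endpoint's model.

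The cost is a change of SAP wording and slightly different denominators between endpoints, which each table should show. ADAS-Cog 11 power is unaffected.

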#### 6. General Issues for Statistical Analysis

[figure not shown]
Table and figure outputs based on the Safety Population and all listings will be presented by actual treatment received. Table and figure outputs based on the PK Population will be presented by actual treatment received. Table and figure outputs based on the mITT Population and Completer Population will be presented by randomized treatment.

Generally, all table and figure outputs will present individual CT1812 dose groups (100 mg, 300 mg) and the pooled CT1812 dose group (100 mg and 300 mg together) in addition to placebo.

#### 6.1. Statistical Definitions and Algorithms

#### 6.1.1. Baseline

The last non-missing observation recorded on or before the first dose of study drug will be used

as the baseline observation for all calculations of change from baseline.

#### **6.1.2.** Adjustments for Covariates

The efficacy models will include APOE  $\varepsilon 4$  (+ or –) status at baseline as covariates. Participants with ambiguous APOE results will be classified as positive for the efficacy analyses.

#### 6.1.3. Multiple Comparisons

Although all of the clinical efficacy analyses for this study are exploratory in nature, the ADAS-Cog 11 least square mean change from baseline analysis is considered the primary exploratory analysis of interest compared to the other clinical efficacy analyses. The primary exploratory analysis of the ADAS-Cog 11 will compare the least square mean change from baseline value for the two active arms combined to the least square mean change from baseline value for the placebo arm at day 182, using a two-sided test at the alpha=0.05 level of significance. If the primary exploratory analysis of the ADAS-Cog 11 is statistically significant, then the following comparisons will be made using the least square mean change from baseline values and the same model as for the primary analysis:

- 1) 300 mg CT1812 versus placebo;
- 2) 100 mg CT1812 versus placebo.

Each comparison will be conducted using a two-sided test at the alpha=0.05 level of significance. This fixed sequence testing procedure will control the overall level of significance for this outcome.

All other clinical efficacy analyses will be conducted using two-sided tests at the alpha=0.05 level of significance. No adjustments will be made for multiple comparisons and all other p-values will be considered nominal.

[figure not shown]
#### 6.1.4. Handling of Dropouts or Missing Data

If a participant is missing one, two, or three individual components of the Cognitive Composite score at a time point, the Cognitive Composite score will be computed using the average of the participant's non-missing components at the time point. If a participant is missing four or more individual components at a time point, the Cognitive Composite score will not be derived at that time point.

For the interim analysis, missing data for endpoints assessed at multiple time points will be imputed using the last observation carried forward (LOCF) approach.

For the final analysis, missing data for endpoints assessed at multiple time points and analyzed using repeated measures models will not be imputed. Missing data for endpoints assessed at post baseline timepoints may be imputed using LOCF for the purpose of analyzing data using an Analysis of Covariance (ANCOVA) model when the MMRM model fails to converge.

For the interim and final analyses, missing data for endpoints assessed at only one post-baseline time point will not be imputed.

#### 6.1.5. Outlier Values and Values below the Limit of Quantitation

Some biomarker analyses may require removal of participants whose values are outliers or who have values at certain time points that are below the limit of quantitation. Decisions regarding inclusion or exclusion of participant values at particular timepoints will be made prior to database lock (DBL) and unblinding of data.

